### 8.1.1.2 Bullous Pemphigoid Disease Area Index

Bullous Pemphigoid Disease Area Index is a clinician completed tool that is used for independent disease severity assessment to measure disease extent in BP ([Wijayanti et al 2017](#)).

The Investigator will be required to complete the BPDAI on a tablet at screening (Visit 1), randomization (Visit 2), and then at each visit until the end of the double-blind treatment period, at the time of presentation with relapse or suspected relapse, at unscheduled visit, and at IPD/end of treatment and follow-up visit.

During the subsequent OLE (if applicable), the Investigator is required to complete BPDAI Q4W, at unscheduled visits (eg, in the event of a relapse), and at the IPD/end of treatment and follow-up visit.

The BPDAI tool computes 2 scores: total BPDAI activity and total BPDAI damage. The total BPDAI activity score (0 to 360) is the arithmetic sum of the 3 subcomponents – cutaneous blisters/ erosions, cutaneous urticaria/erythema, and mucosal blisters/ erosions. The total BPDAI damage score (0 to 12) is the arithmetic sum of the items rated regionally for damage caused by more permanent features such as post-inflammatory hyperpigmentation, scarring and other. BPDAI quantifies lesion number and size thresholds. Lesions are rated based on the regions affected. BPDAI gives additional weighting to areas of the skin primarily affected in BP, such as the limbs, and less emphasis to scalp and face. The BPDAI total activity and BPDAI damage give an indication of disease activity, with higher scores indicating greater disease activity or damage.

#### **8.1.1.3      Investigator Global Assessment**

[figure not shown]
An IGA scale uses clinical characteristics to assess overall disease severity at any given time point. This scoring system allows clinicians to rate skin disease activity by general overall impressions. This IGA scale uses key signs of BP with ordinal levels of severity. The IGA is a 5-point categorical scale ranging from 0 (clear) to 4 (severe) with higher scores indicating greater disease activity or damage ([Table 7](#)). The IGA uses clinical characteristics based on the number of lesions, blisters, erosions, erythema and number of anatomical locations. The IGA scale will be completed at the site by the investigator according to the SoA ([Table 2](#)).

**Table 7      IGA Scores and Descriptions**

Score	Description
0 – Clear	No skin lesions
1 – Almost Clear	Very few small skin lesions
2 – Mild	Few skin lesions
3 – Moderate	Multiple lesions in > 1 anatomical area OR any large erosive area
4 - Severe	Extensive skin lesions/erosive areas

Note: Examples of skin lesions include blisters, small round erosions, and erythema.

CCI

#### **8.1.1.7 Healthcare Resource Utilization**

Broad-based all-cause and BP-related healthcare resource utilization information will be collected by the Investigator, or designee, in accordance with the SoA ([Table 2](#)) and recorded in the appropriate eCRF module. Protocol-mandated procedures, tests, and encounters are not included.

At randomization, retrospective all-cause and BP-related healthcare resource utilization information will be collected with a one-year recall period. At all subsequent visits, all-cause and BP-related healthcare resource utilization information will be collected with a recall period of ‘since last scheduled visit’.

The data collected may be used to conduct exploratory economic analyses and include:

- Number and duration of medical care encounters, including surgeries, and other selected procedures (inpatient and outpatient)
- Duration of hospitalization (total days or length of stay, including duration by wards [eg, intensive care unit])
- Outpatient medical encounters and interventions (including specialist visits, General Practitioner visits, home health care visits, and emergency room visits, etc.)
- Number and type of diagnostic and therapeutic tests and procedures

CCI

### **8.1.2 Patient-reported Outcomes**

Participants will complete all PRO assessments using provisioned devices. All participants will complete PROs on the tablet at onsite visits. Daily PROs are completed on the handheld device at home. If the Investigator believes that the participant has a medical condition (eg, BP skin lesions on the fingers/hand, neurologic condition affecting the fingers/hand, or severe visual impairment), then an exemption from at-home PROs may be requested from the AstraZeneca study physician prior to the screening visit.

The Investigator will ensure that participants are properly trained on the use of the handheld PRO device and the importance of completing at-home assessments as scheduled. Compliance should be checked weekly (at a minimum) to ensure that the participant is completing the assessments as scheduled, including a check of the daily oral steroid doses taken. The Investigator or designee will be responsible for monitoring participant adherence with the daily assessments and follow up as necessary.

The at-home handheld device will be programmed at Visit 2 with reminder alarms for the daily questionnaires. Study site staff will be able to adjust alarms for specific participant needs as needed. The participant will be required to complete a training module before taking the device home.

Participants must bring the at-home handheld device to every visit.

Confirmation of the visit in the PRO system, completion of at-site PRO assessments, and review of participant compliance with at-home PRO assessments should be completed prior to other study procedures. The timing and frequency for each PRO is provided in [Table 3](#). The handheld device will be returned to the study site at Visit 22 (Week 72) or at the IPD visit for participants who prematurely discontinue from IP and are unwilling/unable to continue with visit procedures.

#### **8.1.2.1 Peak Pruritus Numeric Rating Scale**

The Peak Pruritus Numeric Rating Scale (NRS) is a one-item assessment that asks participants to rate the intensity of their worst itch during the past 24 hours. The scale ranges from 0 (no itch) to 10 (worst itch imaginable).

The participant will complete the Peak Pruritus NRS on a provisioned handheld device at home according to the schedule in [Table 3](#).

### **8.1.2.2 Corticosteroid Medication Usage**

The participant will be asked to report the dosage of OCS taken over the past 24 hours.

The participant will complete the Corticosteroid Medication Usage question on a provisioned handheld device at home according to the schedule in [Table 3](#).

Patient-reported corticosteroid use and dosage will be checked at each clinic visit/telephone contact visit. This check should include a review of compliance with the prescribed OCS dose between each visit and/or tapering of dose, as described in Section [6.5.1](#).

### **8.1.2.3 Bullous Pemphigoid Disease Area Index Pruritus**

The BPDAI-Pruritus is a separate component of the BPDAI that asks the participant to grade the severity of pruritus over the past 24 hours, the past week, and the past month. For each recall period, severity of pruritus is rated on an NRS ranging from 0 for no itch to 10 for maximal itching. The three scores are then summed for a total score ranging from 0 to 30.

The participant will complete the BPDAI-Pruritus on a tablet at the site as per schedule of assessments ([Table 2](#)).

### **8.1.2.4 Autoimmune Bullous Disease Quality of Life Questionnaire (AB-QoL)**

The AB-QoL is a 17-item assessment of the health-related quality of life impact of autoimmune bullous diseases, including BP. The recall period is one week. The participant will complete the AB-QoL on a tablet at the site as per schedule of assessments ([Table 2](#)).

### **8.1.2.5 European Quality of Life-5 Dimensions (EQ-5D-5L)**

The EQ-5D-5L questionnaire assesses 5 dimensions: mobility, self-care, usual activities, pain/discomfort and anxiety/depression. Each dimension has 5 response options (no problems, slight problems, moderate problems, severe problems, and extreme problems) that reflect increasing levels of difficulty.

The participant will be asked to indicate his/her current health state by selecting the most appropriate level in each of the 5 dimensions. The questionnaire also includes a visual analog scale, where the participant will be asked to rate current health status on a scale of 0 to 100, with 0 being the worst imaginable health state.

The participant will complete the EQ-5D-5L on a tablet at the site as per schedule of assessments ([Table 2](#)).

### **8.1.2.6 Qualitative Patient Interview Sub-study**

Participants who complete the ICF in select languages, and one primary caregiver (if applicable), will be invited to participate in a qualitative patient interview sub-study. Up to 34 participants (or participant-caregiver dyads) will be enrolled in the sub-study. The

sub-study consists of interviews at 3 timepoints (prior to treatment/early treatment, end of double-blind treatment, and after at least 6 months of OLE). The interviews will be non-interventional and will collect data on participants' experiences with BP and the study treatment, and the participants' conceptions of meaningful change on some of the PROs used in this study. If a caregiver can participate, the caregiver's perspective will be included to better understand the familial and social burdens of the disease. Interviews will be conducted remotely (eg, by telephone) at a time convenient for the participant and/or caregiver; they will not be conducted during the course of a site visit. The duration of each interview will be approximately 90 minutes.

A detailed description of sub-study procedures is available in the Qualitative Patient Interview Sub-Study Manual.

Participants will be introduced to the sub-study during the informed consent process using the participant communication materials attached to the Qualitative Patient Interview Sub-study Manual. Interested participants and/or caregivers will consent specifically for this sub-study (participation in this sub-study is optional and independent from the main study). Participants and/or caregivers will be contacted according to procedures described in the Qualitative Patient Interview Sub-study Manual.

Each sub-study participant will be interviewed at the following timepoints:

- Prior to treatment/early treatment: between Week 0 and Week 4, to capture experiences before starting study treatment and/or in the first month of study treatment
- End of double blind: between Week 28 and Week 36, to examine participants' experiences during study treatment
- Open-label extension: between Week 60 and Week 76, to examine participants' experiences with BP in the open label period

During each interview, participants (and caregivers, if applicable) will be asked a set of open-ended questions. The interview discussion guide is provided as an appendix to the Qualitative Patient Interview Sub-study Manual.

The interview will be audio recorded with the participant's permission (and caregiver's permission, if applicable), confirmed verbally prior to the start of the interview. The recordings will be transcribed, and transcripts will be coded using qualitative data analysis software.

Participants' and caregivers' confidentiality and personal information will be protected throughout the sub-study to the same standard as all other coded data in the study.

Due to the qualitative nature of the data and the analysis, the results will be presented in a separate report (ie, not in the Clinical Study Report [CSR]) and the data (transcriptions) will not be entered into the study database. No identifiable data will be reported.

AstraZeneca will follow standard procedures for handling AE reporting involving these participants (as described in [Appendix B](#)). At the beginning and end of each interview, participants will be advised to report any AE to the Investigator or designee.

## **8.2 Safety Assessments**

Planned time points for all safety assessments are provided in the SoA ([Table 2](#)).

### **8.2.1 Physical Examinations**

Physical examinations (complete or brief), including height and weight, will be conducted in accordance with the schedule provided in [Table 2](#). Baseline measurements will be assessed at screening (Visit 1) or the randomization visit (Visit 2) before first dose of IP. Any new findings or aggravated existing abnormalities, judged as clinically significant by the Investigator, will be reported as an AE as described in Section [8.3.5](#).

The complete physical examination will include an assessment of the following: height and weight, general appearance, skin, head and neck (including eyes, ears, nose, mouth, and throat), lymph nodes, abdomen, musculoskeletal (including spine and extremities), cardiovascular, respiratory, and neurological systems.

The brief physical examination will include an assessment of the following: weight, general appearance, skin, abdomen, cardiovascular, and respiratory system. For the brief physical examination, only information on whether the assessment was performed or not is to be recorded. Weight measurements will be performed in light clothing and without shoes and will be recorded in kilograms.

### **8.2.2 Vital Signs**

Pre-dose vital signs (pulse rate, blood pressure, respiratory rate, and body temperature) will be assessed in accordance with the SoA ([Table 2](#)).

It is recommended that vital signs are assessed before any interventional study procedures (blood test collection, IP administration).

Body temperature will be measured in Celsius in accordance with local standards.

Blood pressure and pulse measurements will be assessed while sitting with a completely automated device. Manual techniques will be used only if an automated device is not available. The pulse rate and blood pressure will be measured after the participant has been

resting for at least 5 minutes in a quiet setting without distractions (eg, television, cell phones). The pulse rate should be obtained before blood pressure.

The respiration rate will be obtained after the participant has been resting for at least 5 minutes, by counting the number of breaths (how many times the chest rises) for one minute.

### **8.2.3      Electrocardiograms**

Single 12-lead ECG will be obtained locally during screening ([Table 2](#)) using an ECG machine that automatically calculates the heart rate and measures PR, QRS, and QT intervals. The ECG results will be interpreted locally.

The Investigator or authorized delegate will be responsible for the overall interpretation and determination of clinical significance of any potential ECG findings. The ECG printouts will be signed and dated by the Investigator and stored at the study site. Any findings will be recorded in the eCRF.

ECG will be taken in the supine position, after the participant has been resting for at least 5 minutes. The assessment should be performed before interventions with the participant (eg, IP administration).

### **8.2.4      Clinical Safety Laboratory Assessments**

[Table 8](#) lists the clinical safety laboratory tests to be performed. Refer to the SoA ([Table 2](#)) for the timing and frequency. All protocol-required laboratory assessments, as defined in the table, must be conducted in accordance with the Laboratory Manual and the SoA ([Table 2](#)).

The Investigator should make an assessment of the available results with regard to clinically relevant abnormalities. The laboratory results should be signed and dated and retained at the site as source data for laboratory variables.

For information on how AEs based on laboratory tests should be recorded and reported, see Section [8.3.5](#).

Additional safety samples may be collected if clinically indicated at the discretion of the Investigator. The date, time of collection, and results (values, units, and reference ranges) will be recorded in the participant's medical records.

The clinical chemistry, and hematology assessments will be performed at a central laboratory, and at both local and central laboratories at Visit 1.

Instructions for sample collection, processing, storage, and shipment are provided in the central laboratory manual.

**Table 8      Laboratory Safety Variables**

Clinical chemistry		Hematology
Alkaline phosphatase	Gamma-GT (gamma-glutamyl transpeptidase)	Hematocrit
ALT (alanine aminotransferase)	Glucose	Hemoglobin
AST (aspartate aminotransferase)	Phosphorus	
BUN (blood urea nitrogen)	Potassium	Platelet count
Calcium	Sodium	
Chloride	Total bilirubin	WBC count (absolute and differential) a
CO 2 (carbon dioxide) b	Uric acid	HbA1c c
Creatinine	Creatinine kinase	
Cholesterol, total		

a Eosinophil, basophil, and monocyte counts will be redacted from the central laboratory reports starting from Visit 2 (see Section 6.3.2).

b Measured as bicarbonate.

c Refer to the schedule of assessments (Table 2) for details of HbA1c.

#### **8.2.4.1      Pregnancy Tests**

The following tests are applicable to female participants only and will be conducted in accordance with the SoA (Table 2).

- FSH: To be performed at Visit 1 only for female participants < 50 years who have been amenorrhoeic for ≥ 12 months prior to the planned date of randomization to confirm postmenopausal status. This test is to be sent to and analyzed at the central laboratory; all females should be treated as pre-menopausal until results are received from the central laboratory.
- Urine human chorionic gonadotropin (HCG; dipstick): To be performed locally at the study site according to the SoA for all female participants except for those who are NOT of childbearing potential as defined in inclusion criterion 7(c). A positive urine pregnancy test result must be confirmed with a serum pregnancy test (beta-HCG).

#### **8.2.4.2      Serology**

Hepatitis B surface antigen and hepatitis C antibody tests will be assessed in accordance with the SoA (Table 2). The testing may be performed at the study site for participants who require immediate results for randomization, however this will also require confirmatory tests sent to the central laboratory. The test to be performed at the central laboratory for all other participants.

In case of positive result of hepatitis B surface antigen or hepatitis C virus antibody, additional testing (eg, hepatitis C ribonucleic acid [RNA] polymerase chain reaction test) may be performed.

HIV-1 and HIV-2 antibodies (along with p24 antigen): Local HIV express test will be performed at Visit 1 to inform eligibility; the sample from Visit 1 will also be sent to the central laboratory. If, after randomization, the result of the central laboratory HIV test is positive, the participant will be discontinued from treatment.

Instructions for sample collection, processing, storage, and shipment are provided in the laboratory manual.

### **8.3 Adverse Events and Serious Adverse Events**

The Principal Investigator is responsible for ensuring that all staff involved in the study are familiar with the content of this section.

The definitions of an AE or SAE can be found in [Appendix B](#).

AEs will be reported by the participant (or, when appropriate, by a caregiver, surrogate, or the participant's legally authorized representative).

The Investigator and any designees are responsible for detecting, documenting, and recording events that meet the definition of an AE or SAE. For information on how to follow up AEs see Section [8.3.2](#).

Care will be taken not to introduce bias when detecting AEs and/or SAEs. Open-ended and non-leading verbal questioning of the participant is the preferred method to inquire about AE occurrences.

#### **8.3.1 Time Period and Frequency for Collecting AE and SAE Information**

All AEs will be collected starting from Visit 1, throughout the treatment period, and including the follow-up period last contact with participant.

Serious AEs will be recorded from the time the participant signs the ICF, throughout the duration of the study. All SAEs will be recorded and reported to the AstraZeneca representative or designee within 24 hours, as indicated in [Appendix B](#). The Investigator will submit any updated SAE data to the AstraZeneca representative within 24 hours of it being available.

If the Investigator becomes aware of an SAE with a suspected causal relationship to the investigational medicinal product that occurs after the end of the clinical study in a participant

treated by him or her, the Investigator shall, without undue delay, report the SAE to the AstraZeneca representative.

### **8.3.2 Follow-up of AEs and SAEs**

After the initial AE/SAE report, the Investigator is required to proactively follow each participant at subsequent visits/contacts. All AEs will be followed until resolution, stabilization, the event is otherwise explained, or the participant is lost to follow-up.

Any AEs that are unresolved at the end of the study (final DBL) will be followed-up by the Investigator for as long as medically indicated, but without further recording in the eCRF. AstraZeneca retains the right to request additional information for any participant with ongoing AE(s)/SAE(s) at the end of the study, if judged necessary.

#### **Adverse Event Variables**

The following variables will be collected for each AE:

- AE (verbatim)
- The date when the AE started and stopped
- Maximum intensity
- Whether the AE is serious or not
- Investigator causality rating against the IP (yes or no)
- Action taken with regard to the IP
- AE caused participant's withdrawal from study (yes or no)
- Outcome

In addition, the following variables will be collected for SAEs:

- Description of AE
- Date AE met criteria for SAE
- Date Investigator became aware of SAE
- AE is serious due to (see definition of SAE in [Appendix B 2](#))
- Date of hospitalization
- Date of discharge
- Probable cause of death
- Date of death
- Autopsy performed
- Causality assessment in relation to study procedure(s)
- Causality assessment to other medication

### **8.3.3 Causality Collection**

The Investigator will assess causal relationship between IP and each AE, and answer ‘yes’ or ‘no’ to the question ‘Do you consider that there is a reasonable possibility that the event may have been caused by the investigational product?’

For SAEs, causal relationship will also be assessed for other medication and study procedures. Note that for SAEs that could be associated with any study procedure, the causal relationship is implied as ‘yes’.

A guide to the interpretation of the causality question is found in [Appendix B](#).

### **8.3.4 Adverse Events Based on Signs and Symptoms**

All AEs spontaneously reported by the participant or care provider or reported in response to the open question from the study site staff: ‘Have you had any health problems since the previous visit/you were last asked?’ or revealed by observation will be collected and recorded in the eCRF. When collecting AEs, the recording of diagnoses is preferred (when possible) to recording a list of signs and symptoms. However, if a diagnosis is known and there are other signs or symptoms that are not generally part of the diagnosis, the diagnosis and each sign or symptom will be recorded separately.

### **8.3.5 Adverse Events Based on Examinations and Tests**

The results from the protocol-mandated laboratory tests and vital signs will be summarized in the CSR. Deterioration as compared to baseline in protocol-mandated laboratory values and vital signs should therefore only be reported as AEs if they fulfill any of the SAE criteria, are the reason for discontinuation of treatment with the IP, or are considered to be clinically relevant as judged by the Investigator (which may include but not limited to consideration as to whether treatment or non-planned visits were required or other action was taken with the study intervention, eg, dose adjustment or drug interruption).

If deterioration in a laboratory value/vital sign is associated with clinical signs and symptoms, the sign or symptom will be reported as an AE and the associated laboratory result/vital sign will be considered as additional information. Wherever possible the reporting Investigator uses the clinical, rather than the laboratory term (eg, anemia versus low hemoglobin value). In the absence of clinical signs or symptoms, clinically relevant deteriorations in non-mandated parameters should be reported as AE(s).

Deterioration of a laboratory value, which is unequivocally due to disease progression, should not be reported as an AE/SAE.

Any new or aggravated clinically relevant abnormal medical finding at a physical examination as compared with the baseline assessment will be reported as an AE unless unequivocally related to the disease under study.

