### **8.3.6 Disease Under Study**

Symptoms of disease under study are those which might be expected to occur as a direct result of BP (eg, pruritus, eczematous lesions, urticarial plaques, blisters/bulla, mucosal lesions). Events which are unequivocally due to BP should not be reported as an AE during the study unless they meet SAE criteria or lead to discontinuation of the IP.

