### **8.3.7 Reporting of Serious Adverse Events**

All SAEs have to be reported, whether or not considered causally related to the IP, or to the study procedure(s). All SAEs will be recorded in the eCRF.

If any SAE occurs in the course of the study, Investigators or other site personnel will inform the appropriate AstraZeneca representatives within one day, ie, immediately but no later than 24 hours of when he or she becomes aware of it.

The designated AstraZeneca representative will work with the Investigator to ensure that all the necessary information is provided to the AstraZeneca Patient Safety data entry site within one calendar day of initial receipt for fatal and life-threatening events and within 5 calendar days of initial receipt for all other SAEs.

For fatal or life-threatening AEs where important or relevant information is missing, active follow-up will be undertaken immediately. Investigators or other site personnel will inform AstraZeneca representatives of any follow-up information on a previously reported SAE within one calendar day, ie, immediately but no later than 24 hours of when he or she becomes aware of it.

If the electronic data capture system is not available, then the Investigator or other study site staff reports an SAE to the appropriate AstraZeneca representative by telephone.

The AstraZeneca representative will advise the Investigator/study site staff how to proceed.

The reference document for definition of expectedness/listedness is the Investigator's Brochure for benralizumab.

For further guidance on the definition of an SAE, see [Appendix B](#).

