3.6.6 Healthcare resource utilization

At randomization, retrospective BP-related healthcare resource utilization information will be collected with a one-year recall period. At all subsequent visits (see CSP Table 2), BP-related healthcare resource utilization information will be collected with a recall period of ‘since last scheduled visit’.

The data collected may be used to conduct exploratory economic analyses and include:

- Number and duration of medical care encounters, including surgeries, and other selected procedures (inpatient and outpatient);
- Duration of hospitalization (total days or length of stay, including duration by wards [eg, intensive care unit]);
- Outpatient medical encounters and interventions (including specialist visits, General Practitioner visits, home health care visits, and emergency room visits, etc.);
- Number and type of diagnostic and therapeutic tests and procedures.

Note: Cases of hospitalization occurring after signing of the ICF must be reported as an SAE (CSP Section 8.3).

All available data will be included, regardless of taking rescue medication or withdrawal from study.

Healthcare resource utilisation will be summarized descriptively. Any additional analyses will be performed separately and not form part of this SAP.

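### Protocol 8.3.5 bars AE and SAE reporting of disease-driven laboratory deterioration without exception, contradicting its own opening paragraph and 8.3.1, 8.3.6 and 8.3.7

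*Protocol*

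**What the plan says.** Protocol 8.2.4 refers the reader to 8.3.5 for how adverse events based on laboratory tests are to be recorded and reported. Section 8.3.5 then gives two rules that bear on the same finding.

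- Its opening paragraph says that deterioration in protocol-mandated laboratory values and vital signs "should therefore only be reported as AEs if they fulfill any of the SAE criteria", cause IP discontinuation, or are judged clinically relevant by the investigator.
- A later sentence says: "Deterioration of a laboratory value, which is unequivocally due to disease progression, should not be reported as an AE/SAE". It has no qualifier and no pointer to another section.

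The neighbouring sections read as follows.

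- 8.3.6, on the disease under study: "Events which are unequivocally due to BP should not be reported as an AE during the study unless they meet SAE criteria". The sentence goes on to add IP discontinuation as a second exception.
- 8.3.7: "All SAEs have to be reported, whether or not considered causally related to the IP".
- 8.3.1: "All SAEs will be recorded and reported to the AstraZeneca representative or designee within 24 hours".

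**The concern.** For a laboratory change attributed to BP that is also serious, the protocol tells a site both to report within 24 hours and not to report at all. The prohibition is the more specific instruction, it follows the general one, and it stands in the section to which sites are directed for laboratory findings. A careful reader could take it as an override.

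At stake is the completeness of SAE reporting and, to a lesser degree, of AEs leading to IP discontinuation. Both are main safety outputs (Protocol 9.4.3.1; SAP 4.2.9.1). An SAE left out under this sentence would also miss its 24-hour report.

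**Working it through.** No arithmetic applies: the plan gives no figure on this point and none is needed. The check is to put one finding, a laboratory deterioration clearly attributed to BP, through each provision in three situations.

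| Provision | Meets an SAE criterion | Leads to IP discontinuation | Neither, but judged clinically relevant |
|---|---|---|---|
| 8.3.5, opening paragraph | report | report | report |
| 8.3.5, disease-progression sentence | do not report | do not report | do not report |
| 8.3.6 | report | report | do not report |
| 8.3.7 with 8.3.1 | report within 24 hours | no separate rule | no separate rule |

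1. **Serious finding.** Four provisions (the opening of 8.3.5, 8.3.6, 8.3.7 and 8.3.1) require reporting. One sentence forbids it, and does so expressly for SAEs. The two instructions cannot both be followed.
2. **Finding that leads to IP discontinuation.** The opening of 8.3.5 and 8.3.6 require reporting. The same sentence forbids it.
3. **Non-serious finding that does not lead to discontinuation.** The sentence agrees with 8.3.6. Here it does useful work, keeping ordinary disease activity out of the AE data. The defect is therefore the missing exceptions, not the exclusion itself.

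The reading rests on one inference: that disease progression in 8.3.5 means progression of BP. It is the natural reading, since BP is the disease under study.

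**The case against.** The strongest reply is that the protocol, read as a whole, leaves little doubt. Four provisions require SAE reporting, and a site would have to apply one sentence while ignoring the paragraph above it and the two sections after it. Other rules also shrink the exposed set:

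- When clinical signs accompany the laboratory change, 8.3.5 says "the sign or symptom will be reported as an AE and the associated laboratory result/vital sign will be considered as additional information".
- Serious BP events are reportable under 8.3.6.
- SAP 3.6.6 notes: "Cases of hospitalization occurring after signing of the ICF must be reported as an SAE".
- Eosinophil, basophil and monocyte counts, which a site might link to BP, are redacted from central laboratory reports from Visit 2 (Protocol 6.3.2 and Table 8).
- Central laboratory values are summarized (SAP 4.2.9.2), and reasons for IP discontinuation are recorded and tabulated (Protocol 7.1; SAP 4.2.1).

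Most of this stands, and it is why the point is minor. What remains is an isolated laboratory change, without reportable signs or hospitalization, that meets another SAE criterion or leads to IP discontinuation. Summary tables do not replace 24-hour reporting, and SAP 3.5.2 leaves local laboratory results out of the analysis. That four provisions point one way does not make a direct prohibition in the fifth harmless.

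A reader might infer more than the documents support:

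- **That sites would omit such events.** With four provisions requiring reporting, the text supports only that they could.
- **That omissions would be unbalanced between arms.** Protocol 2.3 expects fewer relapses on benralizumab, but no passage gives a rate or an arm difference for isolated BP-driven laboratory deterioration. If the imbalance existed, missing events would fall mainly on placebo and would make benralizumab look relatively worse on safety.
- **That a size in percentage points can be given.** The documents contain no estimate of how many events would be affected.
- **That the data monitoring committee is the only safeguard.** No safety stopping criteria are preset, but Protocol 7.2.1 lets the sponsor terminate or suspend the study, and Section 8 requires immediate safety concerns to be raised at once.
- **That the physical-examination sentence closing 8.3.5 has the same fault.** It lifts a duty to report findings related to the disease. It does not mention SAEs or forbid reporting, and it reads consistently with 8.3.6.

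**Conclusion.** The contradiction is real and direct: the disease-progression sentence in 8.3.5 is wrong as written. Its consequence is that a serious or IP-discontinuing laboratory deterioration attributed to BP could go unreported, not that it will. Few such events are expected and the documents allow no count, so the point is minor. It has no bearing on power, Type I error or any efficacy analysis.

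The conclusion assumes that disease progression means BP progression. It is also limited by what could be seen. Appendix B, to which the protocol delegates SAE definitions and reporting guidance, was not in the text available. It may settle the matter elsewhere, but 8.3.5 would still give sites a contrary instruction.

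**What to change.** Reconcile the sentence with the protocol's own rule by adding an exception: unless the deterioration meets SAE criteria or leads to discontinuation of IP (Section 8.3.6). This keeps the exclusion for non-serious disease activity and introduces no new policy. The physical-examination sentence at the end of 8.3.5 needs at most a cross-reference to 8.3.6. Check Appendix B for matching wording.

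The cost is one clause, an optional cross-reference and a short reminder to sites. Data collection, endpoints and analyses do not change.
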